#### 4.2. Study Population

All infants with an established diagnosis of BA, excluding those with Biliary Atresia Splenic Malformation syndrome, who are seen at one of the ChiLDREN study sites and who undergo a standard surgical HPE before age 120 days will be eligible for the trial. Parents/guardians will be approached about participation in this clinical trial after a decision is made by the attending physician at the ChiLDREN site for the infant to undergo an exploratory laparotomy with possible HPE, or within 5 days after HPE.

Definition of HPE. Open abdominal surgery in which a Roux-en-Y loop of jejunum is anastomosed to the porta of the liver after a careful surgical dissection to locate patent bile duct remnants in the porta. For purposes of this protocol the term HPE excludes the gall bladder Kasai procedure and excludes laparoscopic HPE.

Definition of BA. For the purposes of this protocol, BA is defined as a fibroinflammatory obliteration of the lumen of one or more segments of the extrahepatic biliary tree within the first 120 days of life. Diagnosis is established at time of surgical exploration by either a) an intraoperative cholangiogram showing blockage of part of or the entire extrahepatic biliary tree or b) failure to be able to perform an intraoperative cholangiogram because of the absence of a gall bladder lumen. Diagnosis is confirmed by surgical exploration of the extrahepatic biliary tree and by subsequent histological examination of the bile duct remnant demonstrating an obstructed or absent lumen. Rarely, post-operative histological examination of the excised biliary remnant will demonstrate that a disease process other

than BA caused the biliary obstruction. If this is found in a subject already enrolled in this trial, the subject will be removed from the study and replaced by another enrollee. In the event that the diagnosis of BA is established during exploratory laparotomy, but the surgeon does not perform a HPE (as may occur in cases of advanced cirrhosis), the patient will not be eligible for this study.

The maximum number of patients to be entered in the study at all clinical sites will be 29 (excluding those replaced because they were found to be ineligible owing to post-op histological information).

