# 4.4.4. Administration of study drug (IVIG)

IVIG will be administered on both an inpatient and outpatient\_basis. Reported adverse events and potential risks are described in Section 7. Appropriate adjustment to the IVIG infusion rate and early termination are described in Section 6. No investigational or commercial agents or therapies other than those described below may be administered with the intent to treat the subject's biliary atresia. If a subject has an acute illness at the time that an IVIG dose is due, the subject will be stabilized medically as per local standard of care before the dose of IVIG is administered. If the 30 day post-HPE visit is missed the 60 day post-HPE dose may still be administered.

Dose and timing: All participants will receive the same dose of IVIG at the same intervals in an open-label fashion as outlined in Table 2 as long as the subject does not have any increased risk for toxicity for any IVIG infusion (see Section 7.4). The day of the HPE will be considered the day that the surgery is completed (the day that the patient leaves the operating room) and this will be called Day 0. The first dose of IVIG will be given on Day 3-5 following the surgery while the subject is still in the hospital. Consent will need to be obtained before the first IVIG infusion.

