### 5.2. Sample size

This Phase 1/2A study is primarily sized based on the precision to estimate the feasibility, tolerability and safety of IVIG in the population of infants with biliary atresia; the sample size of 29 subjects has been calculated, with 20% loss-to-follow-up expected (resulting in 23 subjects). With this sample size, we also calculated the power to compare preliminary efficacy (activity) outcomes between the IVIG subjects in this study and a comparable population of historical controls from another ChiLDREN study.

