#### 5.2.1. Feasibility, Acceptability, Tolerability and Safety

To determine the feasibility, acceptability, tolerability and safety profile of IVIG treatment after HPE for BA (Aim 1), we will determine the proportion of participants who have feasibility, acceptability, tolerability and safety problems with IVIG treatment. For convenience below, we discuss power and precision in terms of adverse events (reflecting the focus on safety), although the same considerations apply to each of feasibility, acceptability, and tolerability. We anticipate that 23-29 subjects will receive IVIG. With this number of treated subjects, we have greater than 98% power to observe at least one subject with a specific adverse event when the true event rate is 20%, 91 to 95% power to observe at least one subject with a specific adverse event when the true event rate is 10%, and 69 to 77% power to observe at least one subject with a specific adverse event when the true event rate is 5%, based on calculations from the binomial distribution.

The power to reject the null hypothesis that the proportion of subjects with either a specific adverse event or any adverse event is 40% or higher, if the true proportion is 10%, 20% or 30% and using a one-sided 10% Type I error rate is provided in Figure 4. With 23 treated subjects, there is 70% power to detect a 40% or higher proportion if the true proportion is 20%, and 79% power to detect this difference with 29 treated patients (exact one-sample binomial test, SAS 9.3). These considerations also apply to the other outcomes described in Aim 1 – feasibility, acceptability and tolerability.

**Figure 4.** Power to Detect Proportion of Outcomes  $\geq$  40%, if the True Proportion is 10%, 20%, or 30% for Various Sample Sizes and one-sided Type I error of 10%

It is important to note that the level used for the null hypothesis in these calculations (40% or higher) is arbitrary and used for purposes of illustration only. Depending on the nature of the adverse event, a much higher rate might well be acceptable if the event is relatively minor and there is clear benefit in terms of lower serum bilirubin or higher survival without liver transplantation, while a much lower rate of a very serious and unusual adverse event might be unacceptable even in the presence of higher survival without liver transplantation.

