## 7.2. Adverse events (AE) and serious adverse event (SAE)

#### 7.2.1. Adverse events (AE) – Overview

IVIG has not been used in infants with BA following HPE to our knowledge. However, IVIG has been used to treat immune deficiencies, Kawasaki disease, neonatal hemochromatosis and idiopathic thrombocytopenic purpura (ITP) in infants and young children previously, and has been tested in small preterm infants as a therapy to reduce the risk for infection and sepsis. In this study, we will monitor for potential adverse effects appropriately at each scheduled visit. Patients will be followed until complete/adequate resolution of an adverse event is documented. We will continue the evaluation of adverse events if a subject withdraws or is prematurely discontinued from participation in the study for any reason. The list of potential expected adverse effects was developed based on information from the package insert of IVIG and reviews of the published clinical trials of IVIG in the diseases mentioned above (45-46). Notably, some of the potential adverse effects of IVIG may also be present in infants with BA due to the natural progression of disease to biliary cirrhosis, such as fever, rashes, and impaired response to routine immunizations. Therefore, it is important in this study that the frequency, severity and seriousness of adverse effects, as well as their likely causality, be assessed in subjects receiving study medication.

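### Section 4.2 lets an infant already given IVIG fall outside the primary safety percentages when histology later rules out biliary atresia

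*Protocol*

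**What the plan says.** **Replacement rule.** Section 4.2 introduces the case with "Rarely, post-operative histological examination of the excised biliary remnant" and gives no expected number. For an infant already enrolled in whom another disease is found, "the subject will be removed from the study and replaced by another enrollee". The ceiling of 29 is then stated as "excluding those replaced because they were found to be ineligible owing to post-op histological information".

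**Timing of exposure.** Section 4.4.4: "The first dose of IVIG will be given on Day 3-5 following the surgery", with day 3 preferred. Under 4.2.1, consent is signed after HPE and within 3 days of it. The protocol does not say when the histology result is due.

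**Removal and follow-up elsewhere.** Section 4.12.2 lists two reasons for removal from the study: withdrawn consent and loss to follow-up. Section 4.12.3 says follow-up per protocol continues after IVIG stops, unless the family or investigator withdraws the infant completely. Section 7.2.1 says: "We will continue the evaluation of adverse events if a subject withdraws or is prematurely discontinued from participation in the study for any reason".

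**Primary safety outcomes.** Section 4.3.1 defines them as percentages of subjects with SAEs, with toxicity of level 3 to 5, and with other expected adverse events. Section 5.3 plans point estimates and one-sided 90% Clopper-Pearson bounds, without saying whether a replaced infant is counted.

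**Aim 1 sizing.** Section 4.1 sets the assessment of feasibility, acceptability, tolerability and safety in 29 enrolled infants. Section 5.2 allows for 20% loss to follow-up, which leaves 23. Section 5.2.1 then says "We anticipate that 23-29 subjects will receive IVIG".

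**The concern.** Safety and tolerability are primary outcomes of this phase 1/2A trial. What IVIG does to an infant is safety evidence whatever the histology later shows, because the infant was dosed under this protocol and carries the same infusion risks. Some of the risks listed in section 7.4, such as delayed hemolysis and transmitted infection, may appear only after the infusion.

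A rule that takes such an infant out of the study and out of the count, with nothing said about the exposure, can leave a toxicity out of the primary percentages. It is also a rule for sites to follow. A site that reads removal as the end of participation may stop collecting adverse events, and a later definition of analysis sets cannot recover data that were never collected.

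**Working it through.** **1. Can a removed infant already have been dosed?** The day of HPE is day 0. Consent comes after HPE and by day 3, and dose 1 falls on day 3, 4 or 5. An infant can therefore be enrolled and undosed for at most about 5 days. Section 4.2 applies to infants already enrolled and sets no condition on dosing. Any histology result that arrives after dose 1 leads to removal after exposure. That this will happen is an assumption, because the date of the result is not stated. That it can happen follows from the text.

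**2. The passages side by side.**

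| Section | What follows for an infant dosed and then found not to have BA |
|---|---|
| 4.2 | Removed, replaced, not among the 29 |
| 4.12.2 | Histology is not among the listed reasons for removal |
| 4.12.3 | Follow-up continues unless the withdrawal is complete; 4.2 does not say whether removal is complete |
| 7.2.1 | Adverse event evaluation continues after discontinuation from the study for any reason |
| 4.3.1, 5.3 | Percentage of subjects; does not say whether this infant is one |

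Section 7.2.1 supports collecting the events. No section puts them into the percentages.

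**3. The plan's own Aim 1 figures.** 29 × (1 − 0.20) = 23.2, so 23.

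- Chance of at least one event, 1 − (1 − p)^n, for n = 23 and n = 29: 99.4% and 99.9% at p = 20% (stated: above 98%); 91.1% and 95.3% at 10% (stated: 91 to 95%); 69.3% and 77.4% at 5% (stated: 69 to 77%).
- Exact one-sample binomial test, null 40%, true proportion 20%, one-sided 10%. For n = 23, reject if X ≤ 5: actual type I error 5.4%, power 69.5% (stated: 70%). For n = 29, reject if X ≤ 7: actual type I error 5.7%, power 79.0% (stated: 79%).

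All the stated figures reproduce.

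**4. Size of the effect on a safety rate.** Let x be the number of infants with an event among the final 29, r the number treated and then replaced, and e the number of those r with an event. The rate under 4.2 is x/29. The rate over all treated infants is (x + e)/(29 + r). The values of x, r and e below are illustrations and do not come from the protocol. With x = 6, the 4.2 rate is 6/29 = 20.7%.

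| r | all replaced infants had an event | none had an event |
|---|---|---|
| 1 | 7/30 = 23.3% | 6/30 = 20.0% |
| 2 | 8/31 = 25.8% | 6/31 = 19.4% |
| 3 | 9/32 = 28.1% | 6/32 = 18.8% |

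For a single replaced infant (r = 1), the shift is (29 − x)/870 upwards if that infant had the event and x/870 downwards if not. Either is at most 29/870 = 3.3 points.

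**The case against.** The best defense is that section 7.2.1 already continues adverse event evaluation after discontinuation for any reason, and this naturally covers an infant removed for histology. Section 7.3 sends all SAEs to the Medical Safety Officer and the DSMB. The list in 4.12.2 does not claim to be exhaustive. The case is rare, and analysis sets may be defined in a statistical analysis plan that is not at hand.

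Much of this stands. It makes it less likely that events go unrecorded, and the expected number of such infants is small. But evaluating an event is not the same as counting it in the primary percentage, and 4.2 places the infant outside the 29. Removal and replacement is also a conduct rule of the protocol, so the protocol should say what it means for exposed infants.

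A reader might infer two stronger things, and the text supports neither.

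- **That infants lost to follow-up are dropped from the primary analysis.** The 20% is a planning allowance. No sentence removes lost infants from a denominator, 4.1 names 29 enrolled infants, and power at 29 is already given. Infants whose family refuses an IV, or whose infusion is stopped, stay in the study (4.4.4, 4.4.5). One could set 23/23 = 100% feasible against 23/29 = 79.3%. That contrast assumes that all six losses come before dose 3, that all six are excluded, and that every other infant succeeds. The protocol says none of this.
- **That safety is biased towards success.** Removal depends on histology, not on tolerability, and the table above shows that the rate can move either way.

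**Conclusion.** The point holds for safety and tolerability counting. As written, 4.2 can put an IVIG-exposed infant outside the primary safety percentages, and it does not fit well with 4.12.2, 4.12.3 and 7.2.1. The consequence is possible omission of toxicity, with no predictable direction for the rate: at most 3.3 points for one such infant, and in the illustration with three, 20.7% against a range of 18.8% to 28.1%. This rests on two assumptions: that some histology results arrive after dose 1, and that sites and analysts apply 4.2 literally.

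The point does not extend to feasibility, acceptability or efficacy. There, a denominator of infants with confirmed BA is defensible, and replacement can stand.

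A minor wording fault remains in 5.2.1. The 23 left after loss to follow-up is presented as the lower end of the number who receive IVIG. Loss during 360 days of follow-up does not undo an infusion already given, and 4.1 speaks of 29. The power figures themselves are correct.

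**What to change.** 1. In 4.2 and 5.3, state that every infant who starts any IVIG infusion counts in the safety and tolerability denominators, including one later found not to have BA. That infant may still be replaced for the feasibility, acceptability and efficacy analyses. The safety denominator may then exceed 29 by the number of treated infants who are replaced.
2. Reconcile the removal wording in 4.2 with 4.12.2, 4.12.3 and 7.2.1, so that a site can tell which follow-up applies to a replaced infant. A reference from 4.2 to the continued adverse event evaluation in 7.2.1 would settle the safety data.
3. In 5.2.1, describe 23 as the number expected to remain after loss to follow-up, not as a number who receive IVIG, and keep the stated power figures.

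The cost is a few sentences, plus adverse event follow-up of a rare extra infant, which 7.2.1 already appears to require. The target of 29 does not change.

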#### 4.2.1. Inclusion criteria

- Infant under 120 days old with established diagnosis of BA and enrolled in the ChiLDREN prospective database study (Prospective Study of Biliary Atresia Epidemiology [PROBE])
- Standard HPE operation has been performed for BA within the previous 3 days
- Post-conception age ≥ 36 weeks at time of enrollment
- Weight at enrollment  $\geq$  2000 gm
- Written informed consent to participate in the study obtained within 3 days of completion of HPE. (Note: Families of potential study subjects may be approached prior to the HPE; however consent can only be signed after the diagnosis of BA is established at surgical exploration and after HPE is performed.)

### 4.2.2. Exclusion criteria

- Laparoscopic HPE or "gall bladder Kasai" (cholecysto-portostomy) surgery was performed
- Biliary atresia splenic malformation syndrome (presence of asplenia, polysplenia or double spleen)
- History of a hypercoagulable disorder
- Renal Disease defined as serum creatinine > 1.0 mg/dl prior to enrollment or presence of complex renal anomalies found on imaging
- Evidence of congestive heart failure or fluid overload
- Presence of significant systemic hypertension for age (defined as persistent systolic blood pressure ≥112 mmHg measured on at least 3 occasions following HPE)
- Infants whose mother is known to have human immunodeficiency virus infection
- Infants whose mother is known to be serum HBsAg or hepatitis C virus antibody positive
- Previous treatment with intravenous immunoglobulin therapy for any reason
- Previous treatment with corticosteroid therapy for post-operative treatment of biliary atresia
- Previous treatment with any other investigational agent
- History of allergic reaction to any human blood product infusion
- Infants with other severe concurrent illnesses, such as neurological, cardiovascular, pulmonary, metabolic, endocrine, and renal disorders, that would interfere with the conduct and results of the study
- Any other clinical condition that is a contraindication to the use of IVIG

# 4.2.3. Inclusion of Females and Minorities

Male and female infants of all races and ethnic groups are eligible for this trial.

### 4.3. Outcome Measures

[figure not shown]
#### 4.3.1. **Primary Outcome Measures**:

- 1. Feasibility: Percentage of subjects for whom administration of IVIG is feasible, defined as the successful administration (at least 80% of each dose) of the 3 doses of IVIG at the prescribed times through peripheral IV lines or central lines if already in place for clinical indications.
- 2. Acceptability: Percentage of subjects for whom the study is acceptable, defined as the ability of the subject's family or guardian to allow intravenous line placements, blood draws, and other study procedures for the study subjects.
- 3. Safety and tolerability measures:
  - a. Percentage of subjects with any serious adverse events (SAEs),
  - b. Percentage of subjects with any level 3, 4, or 5 toxicity (per NCI CTEP grading system [http://www.eortc.be/services/doc/ctc/ctcaev3.pdf], and
  - c. Percentage of subjects with other expected adverse events (such as allergic reactions, irritability, fluid volume problems, IV infiltration and aseptic meningitis).

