
# 1.1. Primary Objective:

# Aim 1: To determine the feasibility, acceptability, tolerability and safety profile of IVIG treatment after hepatic portoenterostomy (HPE) for biliary atresia.

*Hypothesis 1*: Administering IVIG will be feasible, acceptable and well tolerated in infants with BA without significant toxicity.

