# 4.4.3. Consenting for study

Written informed consent will be obtained within 3 days after HPE surgery performed for established biliary atresia. As part of the informed consent process, parents/legal guardians will be informed of the study procedures, the design of the study, the potential risks and benefits of participation and potential side effects of IVIG. This information will be shared with the parent/guardians at the time of enrollment.

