known to be effective for BA or for other diseases and, thus, PK/PD studies would be difficult to interpret. Therefore, we chose to use a high dose of IVIG that is effective in other immune-mediated diseases in children and adults and that should be well tolerated by the infants and their families.

Route of Administration: Dose #1 of IVIG will be administered through peripheral IV, central venous catheter or PICC line, whichever is in place for clinical indications on days 3-5 following HPE. It is mandatory that dose #1 be administered during the inpatient post-operative period following HPE. It is anticipated that doses #2 and #3 of IVIG will be administered in the outpatient setting, although these doses could be administered in the inpatient setting if the subject had been admitted to hospital for a clinically indicated reason. If no IV is in place at the prescribed time for doses #1, #2, or #3 of IVIG, then a peripheral IV will be started for the study drug administration and removed after administration of the IVIG. If the family does not allow placement of a peripheral IV for a dose of IVIG, then that dose of IVIG will not be given but the subject will remain in the study and follow the rest of the study protocol, including attempts at administering subsequent IVIG doses.

IVIG Infusion	Day of dosing following HPE*	IVIG dose**
#1	Day 3 (up to day 5)	1 gm/kg body weight
#2	Day 30	1 gm/kg body weight
#3	Day 60	1 gm/kg body weight

Table 2. Schedule and dosing of IVIG following HPE in infants with biliary atr	esia.
--	-------

\*See 4.4.4 Dose and Timing

\*\*Initial dose will be based on subject's weight at time of HPE. Subsequent doses will be adjusted based on subject's weight measured at 30 and 60 days after HPE. HPE = hepatic portoenterostomy; IVIG = intravenous immunoglobulin

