## 6.2.3. Informed consent process and plan

A common template for the informed consent form will be used at each clinical site with modifications in the format as necessary to meet the requirements of the respective institutional human subjects committees. The parents/guardians will retain a copy of the signed consent form; the original signed consent will be retained in the subject's medical record and a copy will be included in the research records. No collection of data related

to the study or to procedures will be done prior to completion of the informed consenting process.

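### Acceptability, a primary outcome, is conditional on consent, so a high value shows acceptability only among families who had already agreed to the procedures

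*Protocol*

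**What the plan says.** Section 4.3.1 lists acceptability among the primary outcomes: "Percentage of subjects for whom the study is acceptable, defined as the ability of the subject's family or guardian to allow intravenous line placements". The definition goes on to cover sampling of blood and the remaining procedures. The denominator is subjects.

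Entry requires "Written informed consent to participate in the study obtained within 3 days of completion of HPE" (4.2.1), and section 4.4.4 adds: "Consent will need to be obtained before the first IVIG infusion". Section 4.4.3 says that, as part of consent, "parents/legal guardians will be informed of the study procedures, the design of the study, the potential risks and benefits of participation". Section 6.2.3 states that no data collection relating "to the study or to procedures will be done prior to completion of the informed consenting process".

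Hypothesis 1 (section 1.1, repeated in 5.3) reads: "Administering IVIG will be feasible, acceptable and well tolerated in infants with BA without significant toxicity". For Aim 1, section 5.3 fixes the analysis of acceptability as a percentage of subjects with a one-sided 90% Clopper-Pearson lower bound. Neither section 4.3 nor the Aim 1 analysis names a count of families approached or declining.

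Refusal after consent is provided for. "If the family does not allow placement of a peripheral IV for a dose of IVIG" (4.4.4), that dose is skipped and the infant stays in the study. Section 4.12.2 allows withdrawal of consent at any time.

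**The concern.** Consent is itself the first act of accepting the regimen. A family that objects to an infusion soon after surgery, to further IV placements on days 30 and 60, or to the research blood draws can say so at consent, and its infant then never becomes a subject. What remains in the denominator is a group selected on the attribute being measured. The outcome records whether families go on allowing what they have just agreed in writing to allow.

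Hypothesis 1 speaks of infants with BA, and section 2.4 says the results should help decide whether a larger phase 2 or 3 trial is worth considering. Willingness at consent bears directly on that decision, and the planned measure does not see it. A high percentage could be reported as support for Hypothesis 1 both where nearly every family agreed to take part and where most declined.

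**Working it through.** **1. The plan's own Aim 1 figures.** Section 5.2.1 extends its calculations to acceptability.
- Chance of at least one event, 1 − (1 − p)^n, for n = 23 and 29: 99.4% and 99.9% at p = 20%; 91.1% and 95.3% at 10%; 69.3% and 77.4% at 5%. These agree with the stated figures.
- Exact one-sided 10% test of a 40% or higher proportion, with 20% true: reject at 5 or fewer of 23 (attained level 0.054) or 7 or fewer of 29 (0.057). Power is 69.5% and 79.0%, against the stated 70% and 79%.

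The arithmetic reproduces. The point concerns the denominator.

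**2. What the planned statistic estimates.** Write a = P(family allows all procedures | family consented) and c = P(family consents | infant confirmed eligible and family approached). The plan estimates a. Nothing in 4.3 or in 5.3 Aim 1 estimates c.

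**3. The planned result at or near full acceptance.** The one-sided 90% Clopper-Pearson lower bound for x of n is the 0.10 quantile of Beta(x, n − x + 1). When x = n it equals 0.10^(1/n).
- 29/29: 100%, bound 0.10^(1/29) = 92.4%
- 23/23: 100%, bound 0.10^(1/23) = 90.5%
- 28/29: 96.6%, bound 87.2%
- 26/29: 89.7%, bound 78.4%

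None of these depends on c.

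**4. The unreported quantity.** The protocol gives no consent rate, so the first column below is an assumption. The number approached is 29 divided by the rate, rounded. The consent proportion is 29 divided by the number approached, with the same type of bound.

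| Assumed consent rate | Approached | Consent proportion (lower bound) | Planned measure if 29/29 allow | Planned measure if 26/29 allow |
|---|---|---|---|---|
| 90% | 32 | 90.6% (80.3%) | 100% (92.4%) | 89.7% (78.4%) |
| 70% | 41 | 70.7% (59.8%) | 100% (92.4%) | 89.7% (78.4%) |
| 50% | 58 | 50.0% (40.8%) | 100% (92.4%) | 89.7% (78.4%) |
| 30% | 97 | 29.9% (23.8%) | 100% (92.4%) | 89.7% (78.4%) |

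The last two columns are the same in every row. The planned statistic cannot distinguish these situations, and the third column is what would.

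**The case against.** The strongest reply is that the measure does what its definition says. It describes how families of study subjects live with a three-dose regimen, and every Aim 1 outcome is equally conditional on consent. That is fair for feasibility and safety, where consent is not itself the outcome. For acceptability, selection acts on the attribute being measured, so the condition has to appear in the label and in the conclusion.

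Several stronger readings might be inferred, and the protocol does not support them.
- **That the result is bound to be close to 100%.** Much of the burden falls after consent: up to three IV placements, five mechanistic blood draws and visits over 360 days. Families can refuse an IV or withdraw, and section 5.2 plans for 20% loss to follow-up, without saying how much of it would count as non-acceptance. No pass mark is set for acceptability, and section 5.2.1 calls its 40% null arbitrary.
- **That a merged figure gives the true acceptability.** With 58 approached and 26 of 29 allowing everything, 26/58 = 44.8%. Reading this as the share of families who find the regimen acceptable treats every refusal as rejection of the regimen. A family may decline any research, the three-day window after major surgery, or a year of visits.
- **That refusals go unrecorded.** Section 5.4.2 has the coordinating center report recruitment status, and screening counts may sit in manuals that are not shown. What can be said is that the protocol links no such count to acceptability.
- **That PROBE supplies an unselected denominator.** PROBE enrolment (4.2.1) is participation in another study.

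Observed against projected accrual would reveal poor recruitment, but it would not separate few eligible infants from many refusals.

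**Conclusion.** The point stands as a limit on interpretation. As defined, the outcome measures acceptability among enrolled families. A low value would be evidence of poor acceptability. A high value, even 29/29 with its bound of 92.4%, does not by itself support Hypothesis 1 for infants with BA.

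The expected direction is that the planned measure overstates acceptability among all families approached, provided that families who decline would, on average, have been less willing than those who consent. The size cannot be derived from the protocol. The 30% to 90% consent range is illustrative only. Safety, feasibility and the stated power are unaffected. The change is worth making because it is cheap and alters what may be concluded on a named primary outcome.

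**What to change.** In 4.3.1 and 5.3 Aim 1:
1. Relabel the current measure as acceptability among enrolled families and keep its planned analysis.
2. Report beside it the consent proportion: families who consented, divided by families approached whose infants were confirmed eligible after HPE. Give its one-sided 90% Clopper-Pearson lower bound. Confirming eligibility matters because sections 4.2.1 and 4.4.2 allow an approach before surgery, while BA is only suspected.
3. Where a family volunteers it, record the main reason for refusal, keeping refusals of the regimen (IV placement, infusion, blood draws) apart from general or logistical ones.
4. Do not combine the two proportions into one figure. Base the statement on acceptability on both.
5. Keep the count as an aggregate, non-identifying screening tally, and reconcile it explicitly with the bar in 6.2.3 on collecting data before consent. Do not treat PROBE enrolment as the full eligible denominator.

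The cost is a small log at each site, where section 4.12.1 already expects an attempt to enroll every eligible patient. No visit or procedure is added. The acceptability picture may look less favorable.
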